9.1.2.2 Secondary Outcomes

The outcomes defined to meet secondary study objectives are described in [Table 1](#).

Table 1 Outcomes to Achieve Secondary Objectives

Secondary objective	Outcome definition	Number of objective
To evaluate the correlation of sensor collected data with a) patients' self-assessed health status and symptoms (CAT) at baseline and study end, b) lung function and lab values at baseline and study end, c) and with history of mild, moderate and severe exacerbations at study end.	
a) Patients' health status and symptoms at baseline (Day 0) and study end will be measured as the summary score across items of the CAT questionnaire that consists of 8-items in which participants can choose a score from 0 to 5, for each visit
 
b) Lung function will be assessed using plethysmography and lab values including complete blood count (CBC) with differential, blood gas analyses (BGA), procalcitonin and CRP will be assessed as per standard practice at baseline (Day 0) and at study end (for details see Section 9.3)
 
c) number, date of onset and duration of mild, moderate, and severe exacerbations, respectively, during the observation period
	3
Sensor derived data may be related to the CAT score, therefore, an additional objective is to investigate whether changes in physical activity, heart rate, heart rate variability, temperature, respiration rate, cough frequency, and sleep pattern in the 3-month observation period, are associated with changes of the patient self-assessed symptoms (CAT).	
Please see above (3a)
 
During the observation period the CAT score will be obtained on a daily basis. Daily summary score across items of the CAT questionnaire will be computed.
	4
To build a model for predicting patient self-assessed symptoms (CAT) score on daily basis and change in the CAT score (and change of CAT score by 2 points or more considered as MCID) employing sensor collected data on physical activity, heart rate, heart rate variability, temperature, respiration pattern, cough frequency, and/or sleep pattern.	Patients' health status and symptoms at baseline (Day 0) will be measured as the summary score across items of the CAT questionnaire that consists of 8-items in which participants can choose a score from 0 to 5. During the observation period the CAT score will be obtained via a digital application on a daily basis.	5

CCI

Page 1

9.2 Setting

This study will comprise of a population enrolled at internal medicine and pulmonology centers in Germany.

9.2.1 Study Population

The study population will be identified according to the below inclusion and exclusion criteria. For inclusion in the study, all of the following inclusion criteria must be fulfilled:

For participants with COPD:

1. Participants capable of giving signed informed consent, as described in Section 10.1, which includes compliance with the requirements and restrictions listed in the ICF and this protocol
2. Participants ≥ 40 and ≤ 80 years at baseline
3. Diagnosis of COPD stage II to IV (documented post-bronchodilator Forced Expiratory Volume in 1 second (FEV1)/ Forced Vital Capacity (FVC) < 0.7 and FEV1 $< 80\%$ predicted)
4. History of moderate or severe exacerbations (≥ 2 moderate exacerbations or ≥ 1 severe exacerbations in any 12-month time window during last 3 years prior to inclusion and ≥ 1 moderate or severe exacerbations in the last 12 months prior to inclusion, considering that the last 12 months may reflect lower exacerbation rate due to Covid-19 measures)

Company substance code **INN**
MS202559 0001

For participants in the calibration cohort:

1. Participants capable of giving signed informed consent, as described in Section 10.1, which includes compliance with the requirements and restrictions listed in the ICF and this protocol
2. Participants ≥ 40 and ≤ 80 years at baseline

Participants are not eligible for this study if they fulfill any of the following exclusion criteria:

For participants with COPD:

1. Participants who, at the discretion of the Investigator, are unlikely to complete the study or will not be able to provide reliable information for the study
2. Clinically relevant and/or serious concurrent medical conditions including, but not limited to visual problems, severe mental illness or cognitive impairment, musculoskeletal or movement disorders, cardiac disease (e.g., heart failure, arrhythmia [esp. atrial fibrillation and conduction blocks]), lung cancer (currently treated) that in the opinion of the Investigator, would interfere with participant's ability to participate in the study or draw meaningful conclusions from the study
3. Participants with a cardiac pacemaker, defibrillators, or other implanted electronic devices
4. Participants with known allergies or sensitivity to silicon or hydrogel
5. Less than 6 weeks since previous moderate/severe exacerbation

For participants in the calibration cohort:

1. Participants who, at the discretion of the Investigator, are unlikely to complete the study or will not be able to provide reliable information for the study
2. Clinically relevant and/or serious concurrent medical conditions including, but not limited to visual problems, severe mental illness or cognitive impairment, musculo-skeletal or movement disorders, cardiac disease (e.g., heart failure, arrhythmia [esp. atrial fibrillation and conduction blocks]), lung cancer (currently treated) that in the opinion of the Investigator, would interfere with participant's ability to participate in the study or draw meaningful conclusions from the study
3. Participants with a cardiac pacemaker, defibrillators, or other implanted electronic devices
4. Participants with known allergies or sensitivity to silicon or hydrogel
5. Diagnosis of pulmonary disease including, but not limited to COPD, asthma, pulmonary fibrosis, with impact on the lung function and exercise capacity

9.2.2 Definition of Study Cohorts and Description of Devices

Cohorts

A cohort of participants with COPD will be established. This cohort will consist of all eligible patients (based on all inclusion criteria and none of the exclusion criteria, see section 9.2.1) at Day 0 visit. Participants will be enrolled consecutively, based on the scheduled visits occurring in 11 health centers in Germany.

In addition, for device calibration purposes a cohort of non-COPD participants will be established. These participants will be recruited at 1 internal medicine center in Germany.

At the Baseline visit (Day 0), the eligible participants (all inclusion and none of the exclusion criteria) of both cohorts will receive a set of devices (adhesive patch device with sensors and phone).

Devices

The Vivalink wearable device will be used to collect data on physical activity, heart rate, heart rate variability, temperature, respiration pattern, cough frequency and sleep pattern. The model of the Vivalink wearable device that will be used in the study is the same as the CE marked model VV-330 with the addition of temperature monitoring. The new model inclusive of temperature monitoring has not yet received the CE mark. Details of the device are presented in [Table 3](#).

Table 3 Vivalink Wearable Device.

Text in blue italics comes direct from the manufacturer or manufacturer's literature.

Device photo including accessories	
What's Included
  
ECG Recorder (the Patch) x1
 
Adhesives x4
 
Charging Case x1
 
USB Charging Cable x1

Brand Name	Medical Wearable Platform SDK-01
Manufacturer	VivaLNK, Inc.
Name or number of the model(s)/type(s)	Model: VV-330 + temperature monitor
Software version	Planned special release for Merck KGaA,
Accessories	Charging Case, Adhesives (hold the ECG recorder in place during recording), USB Charging Cable + USB electrical outlet adapter
Intended purpose	
Below in italics is the intended purpose of the CE marked Model VV-330 as supplied by VivaLNK. The device to be used in the study, includes a temperature monitoring algorithm not covered by the CE marked device described below.
 
"Medical Wearable Platform SDK-01 is intended to record, store and transfer electrocardiogram (ECG) and accelerometer data. The platform has the capability to provide Heart Rate, Respiratory Rate and R-R Interval using the ECG rhythm. The ECG recorder patch is an ambulatory, continuous recording patch, intended for at-home or hospital, by clinicians or health professionals who intend to monitor their patient's physiological and health conditions for an extended period of time. The device is not intended for patients under 18 years old. This Instructions for Use is only limited to the use of the hardware and the Software Development Kit (SDK). It does not include any information about the mobile application or user interfacing device as that is outside the scope of the system."

The period of validity of CE certificate for model VV-330.	Issue date: 2019-11-08 Expiry Date: 2024-05-26

NOTE: the model to be used in the study has been modified from the CE marked device to add an temperature monitoring algorithm (a software only change).	
Statement of deviation from the CE marked device	The device used in the study will be the same as the CE marked model VV-330 with the addition of temperature monitoring capabilities. A temperature sensor already present in the model VV-330 has been "activated" by the addition of an algorithm. The temperature sensor was already physically present in the wearable patch at the time of the CE mark, but was not turned on, tested or evaluated by the Notified Body for the current CE mark status.
Description of device materials in contact with body tissues	Body-contacting materials are on the Adhesive, which includes proprietary textile and medical-grade adhesive layers with hydrogel conductive contacts.
Statement that this device does not include any medicinal substances, human or animal tissues or their derivatives, or other biological active substances	"Our device does not include any medicinal substances, human or animal tissues or their derivatives, or other biological active substances."
Reference to the compliance of applicable national regulations	VV-330 complies with the EU Medical Device Regulation (MDR) 2017/745 and meets the requirements in Annex1 General Safety and Performance Requirements. The addition of the temperature monitoring algorithm has not yet been evaluated by the Notified Body for conformance.
Describe the necessary training and experience required for the use of the MD.	VV-330 + temperature monitor is intended to be used by adult patients (18 or older) and their health care providers. No special training outside of familiarization of the general instructions from the approved labelling is needed.

LTE Phone (EDGE Device)

An EDGE device serves as a data transmission route from the Vivalink adhesive patch to the clinical database. The EDGE device is a Long-Term Evolution (LTE) phone which functionality is limited to data transfer and to the study software application that includes a questionnaire and the possibility to label events (see above). On this EDGE device a daily CAT questionnaire will be presented to the participant (see Section 9.1.1).

9.2.3 Observation Period

Participants will be followed-up for 3 months (until End of Study visit) or until premature discontinuation from study, whichever occurs first.

Participants in the calibration cohort will be followed-up for 2 weeks.

9.2.4 Frequency of Assessments

An overview of the planned assessments is provided in [Table 4](#) and [Table 5](#).

Company substance code INN
MS202559_0001

COPD cohort

The participants will visit the sites as per routine practice and the timing of the visits and assessments performed will be as per the treating physician judgment. Results of the assessments will be collected upon availability.

Table 4 Planned Assessments: COPD Cohort

Assessments	Baseline Visit Day 0	Exacerbation Visits (moderate and severe)	End of Study 3 Months ± 14 days	Comments
Participant Informed consent	X			
Inclusion/Exclusion criteria	X			
Demographics	X			
Medical history	X			
Physical examination	X	X	X	
COPD history	X			
Baseline Medication	X			
Record changes in medication (COPD and other)		X	X	Changes in medication means changes of medication at the time of the current visit (including newly prescribed medication) as compared to the baseline visit (Day 0)
Comorbidities	X			
Smoking status	X			
Exacerbation history	X			
Moderate and severe exacerbations during observation period		X	X	Moderate and severe exacerbations should be recorded that occurred between Day 0 and the current visit (including exacerbations at the time of the visit)
Lung function (Plethysmography)	X	X	X	For the Baseline visit (Day 0), data from the past 2 weeks are acceptable.
End of study satisfaction questionnaire			X	
(S)AE recording	→			Continuous recording
Serious Adverse Device Effects (SADE) and Device Deficiency (DD) reporting	→			Continuous reporting
CAT collection via App	Daily at home			
Data collection via App (labeling events and activities)	Daily at home			Includes medication data used to identify mild exacerbations

Laboratory values (if available from clinical practice)				For the Baseline visit (Day 0), data from the past 2 weeks are acceptable.
C-reactive protein (CRP)	X	X	X	
Procalcitonin	X	X	X	
Blood count (including eosinophiles, neutrophiles, Hb)	X	X	X	
Capillary blood gas analysis: pO ₂ and pCO ₂ ; SpO ₂	X	X	X	

Table 5 Planned Assessments Calibration Cohort

Assessments	Day 0	End of Study 2 Weeks	Comments
Participant informed consent	X		
Inclusion/Exclusion criteria	X		Assessed by Investigator by review of medical history and/or participant reported medical history
Demographics	X		
Medical history	X		
Comorbidities	X		
Medication	X	X	
End of Study satisfaction questionnaire		X	
(S)AE recording	→		Continuous recording
SADE and DD reporting	→		Continuous reporting
Data collection via App (labeling events and activities)	Daily at home		

9.2.5 Withdrawal from the Study

Participants are free to discontinue the study at any time without giving their reasons. Participants will be withdrawn from study participation for any of the following reasons:

- Informed consent withdrawal
- Participant is unable to handle the devices and has proven to not provide reliable data
- The study is prematurely stopped by the sponsor

9.3 Variables

The following variables will be collected for this study (pending availability):

Several biometric parameters will be measured in a time-dependent manner using the Vivalink wearable device. Values measured from day 8 to 14 will be used as baseline data (e.g. for determining parameter changes during the observation period or as co-factor in model building) unless this time period is within a 2-week distance of an exacerbation. In this case the next 7-day period with a distance of 4 weeks from an exacerbation will be considered the baseline in this context.

Variables measured with the Vivalink wearable device (including, but not limited to):

- Physical activity including stair climbing, (calculated based on continuous accelerometer measurement) [daily average] (derived parameter)
- Heart rate as beats per minute [daily average] (derived parameter)
- Resting heart rate (resting state as determined by accelerometer, beats per minute) [daily average] (derived parameter)
- Heart rate variability reflecting differences in time intervals between 2 R-waves in the ECG (milliseconds) [daily average (where applicable) of the following parameters: SDRR (standard deviation of RR intervals), SDNN (standard deviation of NN intervals), SDNNI (Mean of the standard deviations of all the NN intervals for each 5 min segment of a 24 h HRV recording), RMSSD (Root Mean Sum of Squared Distance), ln(RMSSD) (natural logarithm of RMSSD), pNN50 (percentage of successive RR intervals that differ by more than 50 ms) SI (stress index), LF power (low frequency fraction of HRV, 0.04 – 0.15 Hz), HF power (high frequency portion of HRV, 0.15 – 0.40 Hz), LF/HF (ratio of LF-to-HF power); for details of calculation check see [Shaffer 2017](#)] (derived parameters).
- Temperature [daily average, minimum -maximum values]
- Respiration rate (breath per minute) [daily average, minimum -maximum values] (derived parameter)
- Ratio of inspiration vs expiration time [daily average min-max] (derived parameter)
- Cough frequency (derived parameter)
- Sleep pattern (derived parameter)

Self-measured Variables:

- Self-reported COPD symptoms via the CAT questionnaire
- Self-reported activities (coughing, coughing with sputum production, spray use, non scheduled spray use, eating, going to bed, waking up, walking, climbing stairs, and physical exercise) as collected by the participant app
- Self-reported satisfaction with the study, collected via end of study questionnaire

Covariates (status at the time of Day 0, closest record prior to):

- Demographics data at baseline: (sex, age, height, and weight, race and ethnicity)
- Body mass index will be calculated based on height and weight
- Smoking status (current, ex-, non-smoker)
- Medical history at baseline
 - Date of diagnosis of COPD
 - Number of moderate or severe exacerbations prior to baseline visit (preceding 36 months, in case available)
- Comorbidities at baseline
- Current medication including COPD treatment at baseline
- COPD severity (GOLD stage)

Lung Function and Laboratory variables

(at Day 0, moderate/severe exacerbation visit and End of study visit)

- Body plethysmography parameters: FEV1 [L], FVC [L], FEV1/FVC, TLC [L] (total lung capacity), RV [L] (residual volume), FRC_{pleth} [L] (functional reserve capacity), IC [L] (inspiratory capacity), R_{aw} [kPa s L⁻¹] (=ratio of sRaw to FRC_{pleth}; airway resistance), sR_{aw} [kPa s] (specific airway resistance), VT [L] (mean tidal volume), ERV [L] (expiratory reserve volume), IRV [L] (inspiratory reserve volume). For definitions see [Criée 2011](#).
- Blood gas analysis:(capillary) pO₂ [mmHg], O₂ saturation [%] and pCO₂ [mmHg],
- Serum CRP [mg/l] and serum procalcitonin levels [ng/ml]
- Blood count (CBC with differential); only values that are available with routine blood counts: Hb [g/dL], Hct [%], Erythrocyte count [10⁶/μL], MCV [fL], MCH [pg], MCHC [g/dL], Reticulocytes [x10³/μL] [% (of erythrocytes)], RDW [], platelet count [10³/μL], WBC count [x10³/μL], Lymphocytes [x10³/μL] [%], Monocytes [x10³/μL] [%], Neutrophils [x10³/μL] [%], Eosinophils [x10³/μL] [%], Basophils [x10³/μL] [%]

Derived and transformed data needed for the analysis are described in Section [9.7.1.1](#).

A complete mapping of objectives, outcomes and variables is available in Section [14.1.2](#).

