Specifically, this study aims at predicting 2 target outcomes: acute exacerbations of COPD (AECOPDs) as defined by the GOLD initiative, and the CAT score as a proxy for patients' disease status. The start of an exacerbation within a patient, regardless of how many exacerbations the patient may have experienced before, will be predicted based on sensor data preceding the

exacerbation, and using basic covariates as well. For type of exacerbations, the severe and moderate exacerbations are considered as our main target as these are linked to the need of urgent medical intervention and will predict those as a group, but also separately (distinguish by type), if possible. Mild exacerbations, the relevance of which is currently a subject of investigation in the field, will also be explored.

For the CAT score, the aim is to predict the total score (max = 40) from the sensor data, and changes in the CAT score of ≥ 2 based on the MCID. With this approach, it is aimed to use the model built on sensor data as an objective means to reflect patients' disease status. While for the prediction of exacerbations the aim is to predict them as early as possible, i.e. days before an exacerbation, for the CAT/disease status prediction the aim is to reflect the daily status.

CCI

This study is exploratory in nature and any predictive models will need to be validated in future studies. A future remote patient monitoring (RPM) solution for patients with COPD built on these models will have 2 prime utilities: First, ameliorating or preventing exacerbations and their negative sequelae by early treatment intervention and second, to provide physicians and patients with a highly granular and precise view on the current disease status and past changes. Such information can be used by the treating physician to optimize therapeutic regimens and by the patients to accompany and optimize lifestyle changes. By using a multimodal sensor approach we intend to increase the accuracy of our predictive models beyond what has been described in the literature and thereby increase their clinical utility.

8 Research Question and Objectives

The aim of the study is to investigate the correlation of real-world sensor-derived biometric data obtained via a wearable device with clinical parameters and PROs for monitoring disease activity and predicting exacerbations for patients with COPD.

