9.7.2.1 Primary Objectives

Primary objective 1): To describe the distribution of sensor collected data on physical activity, heart rate, heart rate variability, temperature, respiration rate, cough frequency, and sleep pattern, by severity of COPD exacerbations.

This analysis will be performed on the COPD participants set.

- Sensor collected data on physical activity, heart rate, heart rate variability, temperature, respiration rate, cough frequency, sleep pattern, at baseline (Day 0), in the period Day 8 to Day 14, and shortly prior (14 days prior to, 7 days prior) to, during an exacerbation and after an exacerbation (8 to 14 days after, 2 weeks after, 3 weeks after, up to 4 weeks after an exacerbation) will be reported as mean (SD) and/or median (Interquartile Range) for continuous variables and counts and frequency (%) for categorical variables. The analysis will be done on the group of severe or moderate exacerbations and on exacerbations by type.

Primary objective 2): To predict moderate or severe COPD exacerbations by building a statistical model employing sensor-derived data and demographic and medical covariates.

This objective aims at predicting the occurrence of a severe or moderate exacerbation, in other words, predicting an event out of the combined group of severe and moderate exacerbations. It is desirable to predict an AECOPD as early as possible, therefore dependency of model metrics on the time period before exacerbation will be explored.

As input to the model a number of algorithms (e.g. self-learning algorithms) for obtaining derived parameters such as cough frequency, physical activities and sleep pattern, heart rate variability, temperature, respiration pattern, cough frequency, or sleep pattern will be developed first using the labeling of activities dataset obtained via the app. Said derived features will help to understand the importance of different raw data patterns, so that explanatory models can be built on top of the machine learning algorithms (Molnar 2022), as a way to support rationalization for physicians and regulatory organizations.

Different machine learning algorithms (e.g. gradient boosting, SVMs, K-nn) will be evaluated, and their performance will be assessed by estimating their accuracy, specificity, sensitivity, and area under ROC metrics.

This analysis will be performed on the COPD participants set.

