			
 - Number of moderate or severe exacerbations prior to baseline visit (preceding 36 months, in case available) - Comorbidities at baseline - Current medication including COPD treatment at baseline - COPD severity (GOLD stage) 
Other covariates (Lung Function and Laboratory variables at Day 0, moderate/severe exacerbation visit and End of study visit) from the physician chart:
 
 - Body plethysmography parameters: FEV1 [L], FVC [L], FEV1/FVC, TLC [L] (total lung capacity), RV [L] (residual volume), FRCpleth [L] (functional reserve capacity), IC [L] (inspiratory capacity), Raw [kPa s L-1] (=ratio of sRaw to FRCpleth; airway resistance), sRaw [kPa s] (specific airway resistance), VT [L] (mean tidal volume), ERV [L] (expiratory reserve volume), IRV [L] (inspiratory reserve volume). - Blood gas analysis: (capillary) pO2 [mmHg], O2 [%] saturation and pCO2 [mmHg] - Serum CRP [mg/l] and serum procalcitonin levels [ng/ml] - Blood count (CBC with differential); only values that are available with routine blood counts: Hb [g/dL], Hct [%], Erythrocyte count [$10^6/\mu\text{L}$], MCV [fL], MCH [pg], MCHC [g/dL], Reticulocytes [$\times 10^3/\mu\text{L}$] [% (of erythrocytes)], RDW [], platelet count [$10^3/\mu\text{L}$], WBC count [$\times 10^3/\mu\text{L}$], Lymphocytes [$\times 10^3/\mu\text{L}$] [%], Monocytes [$\times 10^3/\mu\text{L}$] [%], Neutrophils [$\times 10^3/\mu\text{L}$] [%], Eosinophils [$\times 10^3/\mu\text{L}$] [%], Basophils [$\times 10^3/\mu\text{L}$] [%]

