#### 3.4.2 Considerations for potential confounders and effect modifiers

Not applicable. All available features will be considered in the predictive modelling.

For objective 4, smoking status, and other relevant baseline covariates will be forced into the models.

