Different machine learning algorithms will be evaluated, and their performance will be assessed by estimating their accuracy, specificity, sensitivity, and area under ROC metrics. Other usual evaluation metrics such as precision, positive predictive value (PPV), negative predictive value (NPV), F1-score will be computed.

This analysis will be performed on the COPD cohort. Internal cross-validation will be tested.

The following models will be used:

- Logistic regression
- Random Forest
- K-nearest neighbors
- Boosting methods (e.g., Gradient boosting machine, GBM)
- Support vector machines (SVM)

Other methods may be tested.

The development of those models will be based on the machine learning algorithms implementation of scikit-learn (12), a python package designed for predictive data analysis. Other packages may be considered if needed (e.g., H2O (13)).

To optimize the performance of the models, feature extraction and selection algorithms will be used.

Explanatory models will be built on top of the selected machine learning algorithm (14), as a way to support rationalization for physicians and regulatory organizations. Depending on the selected ML model selected, either model specific (for logistic regression, decision trees, k-nearest neighbors) or model agnostic methods will be considered (global methods as PDP, ALE, functional decomposition, and local methods as LIME and Shapley values).

### 3.4.5.3 Secondary Objective 3

Objective 3 will be analyzed on the COPD cohort. For each pair of variables and outcomes ( $x, y$ ) defined below, Pearson's correlation coefficient will be computed together with a 95% asymptotic confidence interval based on Fisher's Z transform.

In case of low variability in parameter values (e.g., exacerbation count), parameters may be treated as ordinal and analyzed in terms of Kendall's Tau statistic with non-parametric confidence interval (see (15)).

The following variable groups and outcomes will be paired and assessed at the indicated time points:

Group x	Group y	Time points for assessment
Sensor data (see section 2.1.4), daily averages (17 variables): physical activity, heart rate, resting heart rate, heart rate variability, temperature, respiration rate, ratio of in- vs expiration time, cough frequency, sleep pattern (hours of sleep)	CAT summary score: Self-assessed patient's health status by CAT questionnaire.	Baseline (Day 0), End of study visit

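### The sensor baseline and visit values allowed as predictors of exacerbations can be recorded after the event's onset, and the SAP sets no time limit on predictors

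*Protocol*

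**What the plan says.** **Baseline.** Protocol 9.3 defines the sensor baseline as Days 8 to 14 and gives its uses as "e.g. for determining parameter changes during the observation period or as co-factor in model building". No objective is named. When that week is within 2 weeks of an exacerbation, it is replaced: "In this case the next 7-day period with a distance of 4 weeks from an exacerbation will be considered the baseline in this context". The severity of the exacerbation is not specified, nor whether distance runs from its onset or its end.

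**Aim.** Protocol section 7 says the start of an exacerbation "will be predicted based on sensor data preceding the" exacerbation, together with basic covariates. Protocol 9.7.2.1 adds that "dependency of model metrics on the time period before exacerbation will be explored".

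**Objective 2 inputs.** The map in protocol 14.1.2 lists, among others, "Other covariates (Lung Function and Laboratory variables at Day 0, moderate/severe exacerbation visit and End of study visit) from the physician chart". It does not list the Day 8 to 14 baseline or its replacement.

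**SAP.** Section 2.3.1 fixes the outcome at the onset date and samples non-event days at least 2 weeks away from any exacerbation. Section 3.4.2 says "All available features will be considered in the predictive modelling". Section 3.4.5.2 names algorithms and metrics and says "To optimize the performance of the models, feature extraction and selection algorithms will be used". It gives no feature window, lead time or requirement that predictors predate onset. Days 8 to 14 appear in the SAP only in the descriptive analysis of Objective 1, and the replacement rule is not repeated.

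**The concern.** A rule suited to describing change, namely finding a quiet week as reference, is also offered as a model input. When an exacerbation comes early, the quiet week can only be found after it. A model for that onset would then hold sensor values that did not exist on the day the prediction is supposed to be made.

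The visit values in the Objective 2 map open a second route. For a given event, the values from its own visit, from later visits and from End of Study are recorded at or after its onset.

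Sensitivity, specificity and AUC are the main output of Objective 2, and the target of 0.85 for sensitivity and specificity drives the sample size. If predictors postdate onset, those metrics answer a different question from the one the protocol asks.

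**Working it through.** **1. The plan's own figures** (protocol 9.5), used here only for scale.
- Events needed: with 18 events and true sensitivity 0.85, at least 13 correct puts the exact one-sided 95% lower limit above 0.50 (tail 0.048). The probability of reaching 13 is 0.958. With 17 events it is 0.901, so 18 reproduces.
- Poisson mean: 60 × 0.5 = 30, and P(at least 18) = 0.993.
- Enrolment: 60 / 0.9 = 66.7, so 67.

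**2. When is the baseline replaced?** Measured from the near edge of the week, 14 + 14 gives onset up to Day 28. A strict reading of the 2-week limit gives Day 27. Requiring the whole week to lie within 2 weeks gives 8 + 14 = Day 22. Moderate or severe exacerbations before entry do not trigger replacement, because protocol 9.2.1 excludes "Less than 6 weeks since previous moderate/severe exacerbation".

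**3. Where can the replacement lie?** A 7-day period ending 28 days before an onset on or before Day 28 would have to end by Day 0. No such week exists after enrolment. The earliest onset with any in-study week (Days 0 to 6) 28 days ahead of it is 6 + 28 = Day 34. So any replacement for an onset up to Day 28 follows the event. For example, a 7-day exacerbation starting on Day 15, with distance counted from its end, gives a baseline of Days 49 to 55.

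**4. The ordinary week.** For onset on Days 1 to 14, Days 8 to 14 do not fully precede the event either.

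**5. Share of events exposed.** Assume a uniform rate over 91 days and 30 expected moderate or severe events.

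| Onset | Share | Events of 30 |
|---|---|---|
| Days 1–28 | 28/91 = 31% | 9.2 |
| of which Days 1–14 (ordinary week also exposed) | 14/91 = 15% | 4.6 |
| of which Days 15–28 (added by the replacement rule) | 14/91 = 15% | 4.6 |
| Days 1–22 (narrowest reading) | 22/91 = 24% | 7.3 |

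For 77 to 105 days of follow-up (3 months ± 14 days), the 28-day share runs from 28/77 = 36% to 28/105 = 27%.

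**6. Early events with no replacement.** A lone early exacerbation leaves room for a replacement week, but a second one can block it. I simulated moderate and severe exacerbations only: Poisson mean 0.5 per 91 days, uniform onset, assumed episode length 0 to 14 days, events within 5 days merged, distance from onset or end. About 10–20% of events with onset by Day 28 had no qualifying week by Day 91. The 31% is therefore an upper figure for events that receive a late baseline.

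**7. Event against non-event days.** A participant's late baseline applies to all of that participant's days, so non-event days are exposed too. On moderate and severe exacerbations alone, 26–32% of events and 18–22% of non-event days are exposed. If mild exacerbations also count, at an assumed 1 per 3 months with zero-length episodes, the figures are about 27% and 25%. At an assumed 2 per 3 months they are about 21% and 25%. The contrast shrinks and then reverses, so none can be relied on.

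**The case against.** **Use in Objective 2 is not planned.** Section 9.3 offers model building as an example and names no objective; Objective 5 also builds models. The Objective 2 map omits this baseline, and the SAP uses Days 8 to 14 only descriptively. This stands: a reader might infer that a leaking baseline is planned, but the documents only permit it. The map does, however, list the visit values outright.

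**Section 7 already limits inputs to preceding data.** It does state the aim, and the SAP is written to reflect the protocol. But section 7 is rationale, and neither protocol 9.3, the map nor SAP 3.4.5.2 turns it into a rule. SAP 3.4.2 and the feature-selection sentence concern which features enter, not when they are recorded. They do not authorise late data, but they do not exclude it.

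**Visit values can be legitimate.** Section 7 predicts each onset regardless of earlier ones, so values from a first exacerbation's visit may properly precede a second event. A reader might infer that all exacerbation-visit values postdate onset. Only those from the event's own or a later visit, and End of Study values, do so.

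**Inflated performance is not shown.** A reader might infer that events are more exposed than non-event days, and hence that the metrics are biased upward. That depends on whether mild exacerbations trigger replacement, which the protocol does not say.

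**The study is exploratory.** Its models need later validation, which limits the consequence. It does not make a post-onset predictor compatible with the stated aim.

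**Conclusion.** The point holds as a gap between the stated aim and the permitted inputs, and it should be fixed. If the section 9.3 baseline, or an event's own or later visit values, enter the exacerbation model as written, that model uses data recorded after onset. Nothing in SAP 3.4.5.2 prevents this.

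Exposure reaches up to 31% of expected moderate or severe events (9.2 of 30), or 24% on the narrowest reading of the 2-week distance. Only half of the 31% is added by the replacement rule. These shares assume a uniform event rate over 91 days at 0.5 per participant. They count moderate and severe events only and do not allow for the early events that get no replacement week. They say nothing about the direction or size of bias. The figures of 18 events, 60 and 67 participants are unaffected.

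**What to change.** In protocol 9.3, the Objective 2 map in 14.1.2 and SAP 3.4.5.2, state the following for predicting exacerbations:

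- Every predictor, including any baseline-referenced sensor feature and the visit values in the map, uses only data recorded before the prediction day. The same rule applies to event and non-event instances.
- Whether a reference week qualifies is judged only on exacerbations that began before that day. Otherwise a missing baseline would itself reveal the coming event.
- Where no earlier week qualifies, the feature is missing and is not filled from that participant's later days. SAP 3.4.4 otherwise allows sensor variables to be imputed.
- A replacement week may be used for a later prediction day that it wholly precedes. Otherwise it serves descriptive and change analyses only.
- State whether the 2-week and 4-week distances run from onset or end, and whether mild exacerbations count.

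**Cost.** Wording only, no new data. With Days 8 to 14 as reference, about 15% of events (4.6 of 30) and about 16–18% of non-event days (simulated) lose baseline-referenced features. For a further 15% of events (onset Days 15 to 28), the reference week lies within 2 weeks before onset, which section 9.3 sought to avoid. Requiring a 14-day gap before onset raises the loss to about 31% of events. Their other pre-event features remain usable.
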